3.0 STUDY DESIGN

This clinical trial is a Phase 2, multicenter, open-label, randomized study evaluating pembrolizumab monotherapy and the combination of acalabrutinib and pembrolizumab in subjects who have recurrent or metastatic NSCLC.

Subjects meeting the eligibility criteria for the study will be randomized 1:1 to one of the following arms:

Arm 1: Pembrolizumab 200 mg administered as an IV infusion every 3 weeks (Q3W)

Arm 2: Acalabrutinib 100 mg administered PO BID plus pembrolizumab 200 mg IV Q3W

Acalabrutinib treatment can continue for subjects who are tolerating therapy and not progressing. Pembrolizumab treatment is for 24 months from the date of first dose for subjects who are tolerating therapy and not progressing. Subjects who progress on the combination of pembrolizumab and acalabrutinib will discontinue study treatment while those with progression of disease in the pembrolizumab monotherapy arm will continue on pembrolizumab with the addition of acalabrutinib until a second disease progression or intolerance to therapy. For subjects who cross over to receive combination treatment, acalabrutinib treatment will begin at the next visit at which subjects are scheduled to receive pembrolizumab. The dose of acalabrutinib for these subjects will be determined based on the DLT review of Arm 2. Disease progression will be determined based on irRECIST guidelines ([Appendix 8](#) and detailed in [Section 3.11](#)).

[figure not shown]
Pembrolizumab treatment can end for subjects with confirmed CR if treatment has been administered for at least 24 weeks and 2 doses of pembrolizumab have been administered after confirmation of CR. Treatment on this protocol can continue for a minimum of 12 months after the last subject is randomized.

All subjects will have hematology, chemistry, and urinalysis safety panels performed at screening. Once dosing commences (Day 1), all subjects will be evaluated for safety, including serum chemistry, serum amylase and lipase, and hematology. PD and PK testing will be performed during the first few months of treatment. Radiologic tumor assessments will be completed at baseline and at ~6-week intervals during the trial. Subjects who discontinue study drug for any reason other than disease progression,

death, lost to follow-up, or withdrawal of consent will be followed for tumor assessment until disease progression or initiation of any other anticancer therapies, whichever comes first.

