3.11 TREATMENT AFTER INITIAL RADIOLOGIC PROGRESSION

RECIST 1.1 will be adapted to account for the unique tumor response characteristics seen with treatment of pembrolizumab. Immunotherapeutic agents such as

pembrolizumab may produce antitumor effects by potentiating endogenous cancer-specific immune responses. The response patterns seen with such an approach may extend beyond the typical time course of responses seen with cytotoxic agents and can manifest a clinical response after an initial increase in tumor burden or even the appearance of new lesions. Standard RECIST may not provide an accurate response assessment of immunotherapeutic agents such as pembrolizumab. Therefore, RECIST 1.1 will be used with the following adaptations:

- If radiologic imaging verifies initial disease progression, tumor assessment should be repeated ≥ 4 weeks later to confirm disease progression with the option of continuing treatment per below.
- If repeat imaging shows $< 20\%$ tumor burden compared to nadir, stable or improved previous new lesion (if identified as cause for initial disease progression), and stable/improved non-target disease (if identified as cause for initial disease progression), treatment may be continued / resumed.
- If repeat imaging confirms disease progression due to any of the scenarios list below, subjects will be discontinued from study therapy (except subjects who cross over to receive acalabrutinib in addition to pembrolizumab).

In determining whether or not the tumor burden has increased or decreased, site study team should consider all target lesions as well as non-target lesions (if needed, the tip sheet provided in the study binder can be used as a reference to assess lesions).

Scenarios where disease progression is confirmed at repeat imaging:

- Tumor burden remains $\geq 20\%$ and at least 5 mm absolute increase compared to nadir
- Non-target disease resulting in initial disease progression is worse (qualitative)
- New lesion resulting in initial disease progression is worse (qualitative)
- Additional new lesion(s) since last evaluation

In subjects who have initial evidence of radiological disease progression, it is at the discretion of the treating physician whether to continue a subject on study treatment until repeat imaging is obtained. This clinical judgment decision should be based on the subject's overall clinical condition, including performance status, clinical symptoms, and

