4.2.3 Immune-related Response Criteria (irRECIST)

RECIST 1.1 will be adapted to account for the unique tumor response characteristics seen with treatment of pembrolizumab. Immunotherapeutic agents such as pembrolizumab may produce antitumor effects by potentiating endogenous cancer-specific immune responses. The response patterns seen with such an approach may extend beyond the typical time course of responses seen with cytotoxic agents and can manifest a clinical response after an initial increase in tumor burden or even the appearance of new lesions. Standard RECIST may not provide an accurate response assessment of immunotherapeutic agents such as pembrolizumab. Therefore, RECIST 1.1 will be used with the adaptations described for irRECIST ([Appendix 8](#)).

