5.5 FUTILITY AND TOXICITY MONITORING

The futility and toxicity monitoring will be analyzed in the combination arm (Arm 2) only as data become available. Futility will be monitored by irDCR, which is defined as irCR, irPR, and irSD by irRECIST ([Appendix 8](#)). irDCR of at least 20% is clinically meaningful in this population. The response outcome within the 12 weeks will be used in the futility analyses. A Bayesian method ([Thall 1995](#)) will be used for futility and toxicity monitoring for the combination arm. The stopping rules are:

- $\Pr(\theta_E < 0.20 | \text{data}) > 0.95$
- Or
- $\Pr(T_E > 0.30 | \text{data}) > 0.90$

Enrollment in the combination arm will be stopped early if there is > 95% probability that the irDCR is < 20% or there is > 90% probability that the toxicity rate is higher than 30% in that arm. Where θ_E denotes the marginal response rate, assuming that θ_E follows a prior distribution of beta (a, b), where a and b represent response and nonresponse

rates (0.2, 0.8), and T_E denotes the marginal toxicity rate, assuming that T_E has a prior distribution of beta (a, b), where a and b represent toxicity and no toxicity (0.3, 0.7). The definition of toxicity will follow the same definition used for assessing DLTs (see [Section 3.7](#)) including the DLT assessment window.

The above futility and toxicity monitoring rules will be implemented once the first 10 subjects have been evaluated in the combination arm and will use safety data as they become available. The corresponding stopping boundaries for the futility monitoring are: enrollment will be stopped early due to futility if (number of subjects with irDCR/number subjects evaluated) \leq 0/(10-15), 1/(16-23), 2/(24-30) and 3/(31-37). The corresponding stopping boundaries for toxicity monitoring are listed in [Table 5-1](#).

The operating characteristics of the design are presented in [Table 5-2](#). Multc Lean software V2.1 was used for the design.

Table 5-1. Stopping Boundaries for Toxicity Monitoring

	Stop enrolling if there are this many DLTs total:
No. Subjects (inclusive)	# Toxicities (inclusive)
1-9	Never stop with this many subjects
10-12	6-12
13-14	7-14
15-17	8-17
18-20	9-20
21-23	10-23
24-25	11-25
26-28	12-28
29-31	13-31
32-34	14-34
35-36	15-36
37	Always stop due to maximum sample size

Table 5-2. Operating Characteristics of the Design

irDCR	Toxicity rate	Probability of early stop	Average # of subjects treated
0.2	0.1	0.23	32.1
0.2	0.3	0.41	28.2
0.2	0.5	0.95	14.8

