At each subsequent tumor assessment, the SPD of the index lesions and of new, measurable lesions ($\geq 5 \times 5$ mm; up to 5 new lesions per organ: 5 new cutaneous lesions and 10 visceral lesions) are added together to provide the total tumor burden: SPDindex lesions + SPDnew measured lesion	
2.0 Follow-up: Recording of Target and New Measurable Lesion Measurements
 
The longest diameters of non-nodal target and new non-nodal measurable lesions, and short axes of nodal target and new nodal measurable lesions will be recorded. Together they determine the Total Measured Tumor Burden (TMTB) at follow-up.
	In alignment with Nishino et al., 2013, unidimensional measurements are used. Measurements of all measured lesions (baseline-selected target lesions and new measurable lesions) are combined into TMTB at follow-up.
	
2.1 Follow-up: Definition of Measurable New Lesions
 
In order to be selected as new measurable lesions (≤ 2 lesions per organ, ≤ 5 lesions total, per timepoint), new lesions must meet criteria as defined for baseline target lesion selection and meet the same minimum size requirements of 10 mm in long diameter and minimum 15 mm in short axis for new measurable lymph nodes. New measurable lesions shall be prioritized according to size, and the largest lesions shall be selected as new measured lesions.
	Proposed selection of up to 5 new measurable lesions of at least 10 mm each versus 10 new measurable lesions as suggested in the irRC criteria is due to the following: 5 new measurable lesions add up at least 50 mm to the TMTB. Since PD is determined by at least a 20% increase in TMTB compared to nadir, this would mean that for irPD assessment the nadir TMTB had to be 25 cm, or 10 cm for 2 lesions in one organ, which is a significant tumor burden already for any cancer patient. That is why measuring up to 5 new lesions in total is sufficient and will not obstruct an irPD assessment. Measuring more than 5 new lesions is not needed. Larger lesions must be preferred as new measurable over smaller lesions, because there will be a greater impact of the TMTB %-increase by these larger lesions for irPD, to support a most conservative approach.

The adaptations from irRC and WHO criteria, as applicable in immunotherapy clinical studies, are documented in the "irRECIST Modifications and Clarifications" column in a comparative table format within our Blinded Independent Central Review (BICR) Charter.

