The modifications we introduce represent adaptations of published criteria based on radiology practice and clinical trial experience, and they provide more objective and reproducible response assessments for investigators and for the central independent image review.

RESULTS

irRECIST criteria are based on irRC criteria adapted for unidimensional measurements, as outlined in Nishino et al., 2013. To further align the criteria with RECIST 1.1 we outline the approach for the assessment of baseline-selected non-target lesions and new non-measurable lesions, and discuss the impact of those lesions on the overall tumor response assessment.

Guidelines for the evaluation of patients with non-target disease only and patients in adjuvant setting is provided.

Original irRC, Including WHO Criteria References	irRECIST Modifications and Clarifications	Rationale for Modification
Non-index lesions at follow-up timepoints contribute to defining irCR (complete disappearance required).	
2.2 Follow-up: Non-Target Lesion Assessment
 
The RECIST 1.1 definitions for the assessment of non-target lesions apply.
 
The response of non-target lesions primarily contributes to the overall response assessments of irCR and irNon-CR/Non-PD (irNN). Non-target lesions do not affect irPR and irSD assessments. Only a massive and unequivocal worsening of non-target lesions alone, even without progress in the TMTB is indicative of irPD.
	Non-target lesions have a subordinate function. In the event that non-target lesions massively progress one cannot ignore such worsening and in these rare cases irPD based only on non-target lesions will be a valid assessment option.
New, non-measurable lesions at follow-up timepoints do not define progression, they only preclude irCR.	
2.3 Follow-up: New Non-Measurable Lesions Definition and Assessment
 
All new lesions not selected as new measurable lesions are considered new non-measurable lesions and are followed qualitatively. Only a massive and unequivocal progression of new non-measurable lesions leads to an overall assessment of irPD for the timepoint. Persisting new non-measurable lesions prevent irCR.
	When new non-measurable lesions substantially worsen in these rare cases irPD based only on new non-measurable lesions will be an assessment option.

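### Section 3.11 and Appendix 8 are presented as one irRECIST progression rule for stopping and crossover, but they conflict for new lesions that keep total tumour burden under +20% of nadir

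*Protocol*

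**What the plan says.** Protocol Section 3.0, in the paragraph on stopping and crossover, states: "Disease progression will be determined based on irRECIST guidelines". It then cites Appendix 8 and says the detail is in Section 3.11. The Synopsis, in the matching paragraph, cites Appendix 8 alone. Section 4.2.3 says "RECIST 1.1 will be used with the adaptations described for irRECIST" and also points to Appendix 8.

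Section 3.11 gives its own list of adaptations to RECIST 1.1. Progression is confirmed at repeat imaging in any of four situations. One is a burden criterion (20% and 5 mm over nadir). The two that concern new lesions are "New lesion resulting in initial disease progression is worse (qualitative" and "Additional new lesion(s) since last evaluation". Neither carries a size. The NOTE near the end of Section 3.11 labels progression confirmed on two scans as being per irRECIST.

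Appendix 8 treats new lesions differently. New measurable lesions are measured alongside the target lesions: "Together they determine the Total Measured Tumor Burden (TMTB) at follow-up". irPD then needs at least +20% and +5 mm in TMTB over nadir. For the remaining new lesions: "Only a massive and unequivocal progression of new non-measurable lesions leads to an overall assessment of irPD for the timepoint". Short of that, they only rule out irCR.

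**The concern.** A site is told that these texts are one rule, yet for a new lesion of modest size they give opposite answers. In Table 3-5 the same repeat scan can fall in the row for confirmed progression (discontinue, no further imaging required) or in the row for stable disease or response (treatment may continue), depending on the definition used.

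The consequence is first about treatment. An Arm 2 subject may be stopped, and an Arm 1 subject may start acalabrutinib, while Appendix 8 still scores irPR or irSD. Two analyses follow from that:

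- **irPFS.** For an Arm 1 subject, time before irPD could include combination treatment. For an Arm 2 subject, scheduled imaging may end before Appendix 8 would call irPD.
- **Crossover objective (Section 2.3).** This concerns subjects who progress on pembrolizumab monotherapy. It would include some who had not progressed by Appendix 8.

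The trial is open-label, response is assessed by the investigator (Section 4.2), and up to 20 centres take part, so an ambiguity in the rule could be resolved differently from site to site.

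**Working it through.** **The plan's own figure.** Appendix 8 (item 2.1) explains how many new 10 mm lesions matter. With k new lesions of 10 mm and stable targets, TMTB reaches +20% when k × 10 ≥ 0.20 × nadir, so nadir ≤ k × 10 / 0.20.

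- k = 5: 50 / 0.20 = 250 mm, the stated 25 cm.
- k = 2: 20 / 0.20 = 100 mm, the stated 10 cm.
- k = 1: 10 / 0.20 = 50 mm.

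The stated figures reproduce. One new 10 mm lesion alone gives irPD only when nadir is 50 mm or less.

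**Rules applied to the same scans.**

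- *Section 3.11:* a new lesion causes initial progression (Table 4-3 gives PD for any new lesion). It is confirmed if that lesion is worse or another new lesion appears. Staying under 20% burden does not undo this, because the continuation condition also asks for the earlier new lesion to be stable or improved.
- *Appendix 8:* irPD if TMTB is ≥20% and ≥5 mm above nadir, or if non-target or new non-measurable disease worsens massively and unequivocally. irPR if TMTB is ≥30% below baseline. Otherwise irSD.

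Lesion sizes are assumed for illustration. Non-target disease is taken as neither complete response nor progression, no worsening is massive, and any growth shown is taken to be read as worse.

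| Case (mm) | TMTB, first and repeat scan | vs nadir | vs baseline | Section 3.11 | Appendix 8 |
|---|---|---|---|---|---|
| Baseline 100; targets 55 then 53; new lesion 10 then 13 | 65, 66 | 65 is nadir; 66/65 = +1.5% | −35%, −34% | confirmed | irPR, irPR |
| Baseline 120, nadir 60; new 10 then 11 | 70, 71 | +16.7%, +18.3% | −41.7%, −40.8% | confirmed | irPR, irPR |
| Baseline and nadir 100; new 10 then 12 | 110, 112 | +10%, +12% | +10%, +12% | confirmed | irSD, irSD |
| Baseline 100, nadir 55; new 10, then a further new 8 (not measurable) | 65, 65 | +18.2%, +18.2% | −35%, −35% | confirmed | irPR, irPR |
| Baseline 100, nadir 60; new non-measurable 6 then 9 | 60, 60 | 0%, 0% | −40%, −40% | confirmed | irPR, irPR |
| Baseline and nadir 40; new 10 then 11 | 50, 51 | +25%, +27.5% | +25%, +27.5% | confirmed | irPD, irPD |

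**Where the disagreement ends.** With stable targets at nadir N and one new measurable lesion of size L (L ≥ 10 mm), Appendix 8 gives irPD once L ≥ 0.20 × N. The 5 mm condition is then met automatically.

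- N = 60: L = 12 gives 72 mm, +20% and +12 mm, so both texts call progression at that scan.
- N = 75: they meet at L = 15.
- N = 100: they meet at L = 20.

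The conflict is therefore a band: a new lesion that has worsened, or a further new lesion, while TMTB stays under +20% of nadir and worsening is not massive.

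**The case against.** The best defence is that Section 3.11 is headed as a treatment section and introduces its list as adaptations of RECIST 1.1, while Appendix 8 scores endpoints. That would settle the matter if the protocol said so. It does not: the Synopsis and Section 3.0 apply Appendix 8 to stopping and crossover, and the Section 3.11 NOTE uses the irRECIST name for its own outcome.

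The defence does limit the consequences. The NOTE allows treatment to continue, after consulting the sponsor, for a subject who is benefiting. Section 3.11 says Arm 1 subjects may be eligible for crossover, which is softer than Section 3.0. Sites also have a tip sheet that is not among the documents, so divergence between sites is a risk and not a shown fact.

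A reader might infer four stronger things that the documents do not support:

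- **The same conflict for non-target disease.** Section 3.11 does list "Non-target disease resulting in initial disease progression is worse (qualitative". But that scenario applies only where non-target disease caused the initial call. Table 4-2 already requires that progression to be unequivocal, and RECIST 1.1 (Appendix 7, 4.3.4) explains this as substantial overall worsening. Appendix 8 item 2.2 adopts the RECIST 1.1 non-target definitions. Both routes start from the same gate.
- **A miscounted futility rule.** Section 5.5 states "Futility will be monitored by irDCR", and its boundaries turn on few subjects (0 of 10–15 up to 3 of 31–37). But it defines irDCR by Appendix 8 alone, as Section 5.4.4 does for the irRECIST versions of DCR and ORR. Section 3.11 assigns no irSD or irPR category. A subject stopped under Section 3.11 and scored irPR is a treatment stop, not a counting error.
- **Disagreement whenever a new lesion worsens above a 50 mm nadir.** The 60 mm example above refutes this.
- **That such cases are common.** The documents give no frequency.

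**Conclusion.** The contradiction is real, and it is confined to new lesions below the Appendix 8 threshold. In that band the same scans are confirmed progression under Section 3.11 and irPR or irSD under Appendix 8, and no section says which governs.

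The direct effect is on when Arm 2 subjects stop, subject to the sponsor-agreed exception, and when Arm 1 subjects cross over. The indirect effect is on irPFS and on who enters the exploratory crossover analysis. The primary endpoint, ORR by RECIST 1.1, does not use irRECIST directly. irDCR for futility and irORR are already tied to Appendix 8.

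The size in subjects cannot be computed. The worked cases rest on assumed lesion sizes and on growth of a few millimetres being read as worse. They show that the conflict exists, not how often it would arise.

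**What to change.** Reconcile the Synopsis (Study Design), Section 3.0, Section 3.11 including Table 3-5 and the NOTE, and Appendix 8, so that one definition of initial and confirmed progression for new lesions is named as governing discontinuation and crossover. Which clinical rule that should be is for the sponsor to decide.

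If the treatment rule is meant to differ from Appendix 8, give it its own name and stop describing its outcome as irRECIST progression. State that irPFS and irDOR, like irDCR and irORR, follow Appendix 8. Censoring detail for subjects who stop or cross over before irPD can sit in the SAP.

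The cost is amendment wording and a revised site tip sheet. Section 3.11 already has irRECIST data collected in the clinical database, so clarifying the definition needs no new scans and no change to the sample size.

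Suggested wording if the sponsor keeps two rules: *Treatment discontinuation and crossover follow the protocol treatment-progression rule in Section 3.11. All endpoints with the prefix ir are derived from recorded lesion data by Appendix 8, whatever the treatment decision.*

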3.12 WITHDRAWAL OF SUBJECTS FROM STUDY TREATMENT

Any subject has the right to withdraw from the study at any time.

- Study treatment should be discontinued in the event of a toxicity lasting > 28 consecutive days, unless reviewed and approved by the medical monitor.
- Any subject who has confirmed objective evidence of cancer progression while receiving acalabrutinib and pembrolizumab should discontinue study treatment.
Note: Study subjects receiving immunotherapies can experience transient immunotherapy-related increases in lesion size (“pseudoprogression”) preceding tumor regression ([Hodi 2010](#)). If there is uncertainty regarding whether there is true cancer progression, the subject may continue study treatment and remain under close observation (eg, evaluated at 4-week intervals) pending confirmation of progression ([Section 3.11](#)). In particular, transient worsening of disease early in therapy or during temporary interruption of study therapy (eg, for drug-related toxicity, surgery, or intercurrent illness) may not indicate cancer progression. In such circumstances, and if medically appropriate, subjects may resume therapy and relevant clinical, laboratory, and/or radiographic assessment can be attempted to document whether tumor control can be maintained or whether cancer progression has occurred.
- Any subject whose medical condition substantially changes after entering the study should be carefully evaluated by the investigator in consultation with the

medical monitor. Such subjects should be withdrawn from study treatment if continuing would place them at risk.

- Any subject who becomes pregnant should be removed from study treatment.
- Any subject who becomes significantly noncompliant with study drug administration, study procedures, or study requirements should be withdrawn from study treatment in circumstances that increase risk or substantially compromise the interpretation of study results.
- The investigator, in consultation with the medical monitor, may withdraw any subject from study treatment, if, in the investigator's opinion, it is not in the subject's best interest to continue.

Subjects who discontinue study therapy will continue to be followed on study for follow-up of safety ([Section 4.3](#)) and survival unless they withdraw consent for further follow-up. Thus, all subjects receiving ≥ 1 dose of study drug will be followed during the immediate post-therapy and long-term follow-up assessments unless the subject withdraws consent for such follow-up to be conducted. The date the subject is withdrawn from study treatment or from the study (including long-term follow-up) and the reason for discontinuation will be recorded and also should be described on the appropriate case report form (CRF).

